6.3.4.1 Follow-up on potential drug-induced liver injury (DILI) cases

Patients with transaminase increase combined with TBIL increase may be indicative of potential DILI, and should be considered as clinically important events.

The threshold for potential DILI may depend on the patient's baseline AST/ALT and TBIL value; patients meeting any of the following criteria must require further follow-up as outlined below:

- For patients with normal ALT and AST and TBIL value at baseline: [AST or ALT > 3.0 x ULN] combined with [TBIL > 2.0 x ULN] OR [INR > 1.5] without evidence of cholestasis (no ALP elevation)
- For patients with elevated AST or ALT or TBIL value at baseline: [AST or ALT > 2 x baseline AND > 3.0 x ULN] OR [AST or ALT > 8.0 x ULN], combined with [TBIL > 2 x baseline AND > 2.0 x ULN]
- For subjects with normal baseline ALT: [ALT \geq 5.0 x ULN]

Medical review must ensure that liver test elevations are not caused by cholestasis, defined as ALP elevation > 2.0 x ULN with R value < 2 in patients without bone metastasis, or elevation of ALP liver fraction in patients with bone metastasis.

Note: (The R value is calculated by dividing the ALT by the ALP, using multiples of the ULN for both values. It denotes whether the relative pattern of ALT and/or ALP elevation is due to cholestatic (R \leq 2), hepatocellular (R \geq 5), or mixed (R > 2 and < 5) liver injury).

In the absence of cholestasis, these patients must be immediately discontinued from study drug treatment, and repeat LFT testing as soon as possible, preferably within 48 hours from the awareness of the abnormal results. The evaluation must include laboratory tests, detailed history, physical assessment and the possibility of liver metastasis or new liver lesions, obstructions/compressions, etc.

1. Laboratory tests must include ALT, AST, albumin, creatine kinase, total bilirubin, direct and indirect bilirubin, GGT, prothrombin time (PT)/INR and alkaline phosphatase.
2. A detailed history, including relevant information, such as review of ethanol, concomitant medications, herbal remedies, supplement consumption, history of any pre-existing liver conditions or risk factors, must be collected.
3. Further testing for acute hepatitis A, B, C or E infection and liver imaging (e.g., biliary tract) may be warranted.
4. Obtain PK sample, as close as possible to last dose of study drug, if PK analysis is performed in the study.
5. Additional testing for other hepatotropic viral infection (CMV, EBV or HSV), autoimmune hepatitis or liver biopsy may be considered as clinically indicated or after consultation with specialist/hepatologist.

All cases confirmed on repeat testing meeting the laboratory criteria defined above, with no other alternative cause for LFT abnormalities identified must be considered as “medically significant”, thus, met the definition of SAE ([Section 8.2.1](#)) and reported as SAE using the term “potential drug-induced liver injury”. All events must be followed up with the outcome clearly documented.

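### Protocol 6.3.4.1, criterion 1: excluding any raised ALP conflicts with the protocol's own definition of cholestasis, so some patients stopped under Table 6-7 miss the DILI evaluation and the named SAE

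*Protocol*

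**What the plan says.** Protocol 6.3.4.1 has three entry criteria.

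- **Criterion 1** covers patients whose ALT, AST and TBIL were all normal at baseline. It needs AST or ALT >3.0×ULN combined with TBIL >2.0×ULN, "OR [INR > 1.5] without evidence of cholestasis", and its parenthesis requires that ALP is not raised: "without evidence of cholestasis (no ALP elevation").
- **Criterion 2** begins "For patients with elevated AST or ALT or TBIL value at baseline" and uses different thresholds.
- **Criterion 3** begins "For subjects with normal baseline ALT" and needs only ALT ≥5.0×ULN, with no condition on ALP.

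The next paragraph asks medical review to rule out cholestasis, "defined as ALP elevation > 2.0 x ULN with R value < 2 in patients without bone metastasis". The action follows: "In the absence of cholestasis, these patients must be immediately discontinued from study drug treatment". The evaluation includes "prothrombin time (PT)/INR and alkaline phosphatase" among its tests, plus a detailed history and a physical assessment. Cases that meet the laboratory criteria, are confirmed on repeat testing and have no other cause are "reported as SAE using the term" for potential DILI.

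Table 6-7 (6.3.1.1) has its own combined row for normal-baseline patients, with the same AST/ALT and TBIL cut-offs. It orders permanent discontinuation unless there is cholestasis, which footnote d defines as ALP >2.0×ULN with R <2. SAP 2.7.3 tabulates potential Hy's law as ALT or AST >3×ULN, TBL >2×ULN and ALP <2×ULN.

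**The concern.** The parenthesis in criterion 1 excludes any ALP above normal. Two definitions in the protocol, and the SAP category, tolerate ALP up to about twice the upper limit. A patient whom the protocol itself would call non-cholestatic can therefore fail criterion 1.

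Raised ALP is plausible here. Exclusion criterion 6 admits ALP up to 1.5×ULN, and criterion 1 asks for normal baseline ALT, AST and TBIL but not ALP. A patient can enter with ALP already raised and be unable to meet criterion 1, read literally, for as long as it stays raised.

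At stake are the completeness of the liver evaluation and the capture of potential DILI as a named SAE. Both study drugs are described as hepatotoxic.

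**Working it through.** The plan states no figure on this point to reproduce. The check applies the protocol's rules as logic, with all values in multiples of ULN and R = ALT/ALP.

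**Inputs.** Criterion 1 read literally: AST or ALT >3, TBIL >2, ALP ≤1. Criterion 1 under the protocol's definition: the same, but with not (ALP >2 and R <2) in place of ALP ≤1. Criterion 3: ALT ≥5. All are from 6.3.4.1; footnote d of Table 6-7 gives the same definition of cholestasis.

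**Step 1, normal baseline with TBIL >2.**

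| ALT | ALP | R | Cholestatic by definition | Criterion 1, literal | Criterion 3 | Result in 6.3.4.1 |
|---|---|---|---|---|---|---|
| 4 | 0.9 | 4.44 | no | met | no | captured |
| 3.5 | 2.0 | 1.75 | no (ALP not >2) | not met | no | missed |
| 4 | 1.5 | 2.67 | no | not met | no | missed |
| 4.9 | 2.4 | 2.04 | no | not met | no | missed |
| 4.5 | 2.4 | 1.88 | yes | not met | no | properly excluded |
| 5 | 1.5 | 3.33 | no | not met | met | captured |

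**Step 2, edges of the gap.** Criterion 3 closes it at ALT ≥5. Below that, the gap is ALP >1 to 2 at any R, or ALP >2 with R ≥2. The second part needs ALT ≥ 2×ALP, so ALT is above 4; with ALT <5, ALP is below 5/2 = 2.5.

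**Step 3, what Table 6-7 does.** Its combined row uses the footnote d definition, so every missed patient with TBIL >2 is permanently stopped. Tests are repeated and LFTs followed weekly. Footnote b's core LFTs do not include INR. For the row ALT 4, ALP 1.5, with TBIL 3, the SAP counts potential Hy's law because ALP <2, yet 6.3.4.1 read literally requires neither evaluation nor the named SAE.

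**Step 4, INR limb.** Assume that criterion 1 groups as AST/ALT with [TBIL or INR]. Take ALT 4, INR 1.8, TBIL 1.2, ALP 1.5. The combined row of Table 6-7 needs TBIL >2, so it does not apply. The isolated rows (ALT >3 to 5; TBIL >1 to 1.5) maintain the dose by default. Criterion 1 fails literally on ALP. Under the footnote d definition it is met, and the patient is stopped and evaluated.

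**Step 5, raised baseline AST/ALT of B (a separate comparison).** Table 6-7 gives min(3B, 5). Section 6.3.4.1 gives min(max(2B, 3), 8). Entry allows B up to 3.

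| B | Table 6-7 | 6.3.4.1 |
|---|---|---|
| 1.2 | 3.6 | 3.0 |
| 1.5 | 4.5 | 3.0 |
| 2 | 5 | 4 |
| 2.5 | 5 | 5 |
| 3 | 5 | 6 |

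**The case against.** The strongest reply is that the parenthesis merely glosses cholestasis, which the section then defines, so a site reading the section as a whole has no gap. That is a reasonable reading, but the text does not state it. The definition is applied by medical review to patients who already meet a criterion. It can remove a patient and cannot bring one back.

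Much of the protection survives when TBIL is >2×ULN: the permanent stop, repeat tests, weekly LFTs, a cyclosporine level for clinically significant elevations (6.3.1.1), weekly follow-up for 4 weeks (6.3.3) and ordinary AE reporting. An investigator may also report an SAE as medically significant under 8.2.1, and the SAP tabulates those with ALP <2×ULN. All of this stands. A reader might infer that the wording leaves these patients on drug; Table 6-7 shows otherwise.

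In the INR limb the loss of the stop is not certain. The >3 to 5×ULN row of Table 6-7 requires discontinuation with evidence of hepatic decompensation, and an INR of 1.8 might be judged to be that. Section 6.3.1.1 requires both drugs to be adjusted or interrupted when their effects cannot be separated. The grouping of the brackets is itself ambiguous. So the automatic stop may be lost, and no more than that can be said.

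A reader might also infer from step 5 that Table 6-7 and 6.3.4.1 contradict each other and that raised-baseline patients could be kept on treatment. The documents do not support that. Both texts order discontinuation, 6.3.4.1 in the absence of cholestasis, so a site obeying both stops at whichever threshold is reached first. What remains is a secondary remark: with B above 2.5, a patient stopped by Table 6-7 at AST/ALT >5 to 2B may not meet the 6.3.4.1 SAE criteria, a band at most 1×ULN wide (2×3 − 5 = 1).

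**Conclusion.** The inconsistency is real and minor. It affects normal-baseline patients with AST or ALT >3×ULN, ALT <5×ULN, TBIL >2×ULN and ALP raised but not cholestatic. They lose the mandated PT/INR, detailed history and physical assessment, and the named SAE. They do not lose the permanent stop. It would be wrong to say that every patient with raised ALP is dropped, because criterion 3 catches ALT ≥5×ULN when baseline ALT was normal.

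For INR >1.5 with TBIL ≤2×ULN, the automatic stop may also be lost, if the brackets group as assumed and the investigator neither finds decompensation nor interrupts both drugs. This should be rare: 7.2.2.5.1 names coagulation testing at baseline, and Table 7-5 lists PT/INR only among tests that may be collected under local practice in follow-up. The laboratory rows of Table 7-1 are not in the text available, so this is an assumption about the first 6 months.

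The conclusion rests on sites applying criterion 1 as written. The documents give no frequency for the pattern. The first-line h-ATG study described in 1.2.1.2.3 reported no case meeting DILI or Hy's law criteria, so few patients are likely. The efficacy decision is unaffected.

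**What to change.** In 6.3.4.1 criterion 1, replace (no ALP elevation) with (i.e. not ALP >2.0×ULN with R <2), and tell sites by memo. This uses the protocol's own definition and narrows no safeguard. The downside is possibly a few more potential-DILI SAE reports. Discontinuations do not increase in the TBIL limb, where Table 6-7 already stops the patient; in the INR limb there may be a rare extra one.

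Leave the raised-baseline thresholds as they are. In particular, do not add a sentence sending anyone who meets either rule to discontinuation and DILI reporting, because it would bypass the condition in 6.3.4.1 that cholestasis is absent. Take baseline ALT 1.5 with normal TBIL, then ALT 4, TBIL 3, ALP 3 (R = 4/3 = 1.33, cholestatic). The Table 6-7 combined threshold of 4.5 is not reached, and 6.3.4.1 orders no stop because of the cholestasis. Such a sentence would permanently stop this patient, whom neither combined rule now stops.

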6.3.1.1 Dose interruption due to liver signals

Eltrombopag dose must be interrupted when clinically indicated. The dose modifications for isolated ALT or AST elevation are listed in [Table 6-7](#). If the dose modification is based on local laboratory, then local laboratory results must be entered in the CRF.

Table 6-7 Criteria for eltrombopag dose adjustment based on liver enzyme and bilirubin levels

Dose modifications for ETB115	
Worst toxicity CTCAE ^a Grade (value) during the treatment	
Investigations (Hepatic)	
Isolated Total Bilirubin elevation	
> ULN – 1.5 x ULN	Maintain dose level
> 1.5 - 3.0 x ULN*	Interrupt dosing and weekly monitor LFTs ^b , or more frequently if clinically indicated, until resolved to $\leq 1.5 \times$ ULN: If resolved in ≤ 14 days, then resume at same dose level If resolved in > 14 days, then decrease one dose level ^e
> 3.0 - 10.0 x ULN**	Mandatory: Interrupt dosing and weekly monitor LFTs ^b , or more frequently if clinically indicated, until resolved to $\leq 1.5 \times$ ULN: If resolved in ≤ 14 days, then decrease one dose level ^e If resolved in > 14 days, then discontinue patient from study drug treatment. LFTs ^b will continue to be monitored weekly, or more frequently if clinically indicated, until total bilirubin have resolved to baseline or stabilization over 4 weeks.
> 10.0 x ULN**	Mandatory: Discontinue patient from study drug treatment The subject should be monitored weekly (including LFTs ^b), or more frequently if clinically indicated, until total bilirubin have resolved to baseline or stabilization over 4 weeks.
* Note: If total bilirubin $> 1.5 - \leq 3 \times$ ULN is due to the indirect (non-conjugated) component only, no changes to dose are required. ** Note: If total bilirubin $> 3.0 \times$ ULN is due to the indirect (non-conjugated) component only, and hemolysis as the etiology has been ruled out as per institutional guidelines (e.g., review of peripheral blood smear and haptoglobin determination), then decrease 1 dose level ^e and continue treatment at the discretion of the investigator	
Isolated AST or ALT elevation	
> ULN - 3.0 x ULN	Maintain dose level

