> 3.0 - 5.0 x ULN	Maintain dose level. Repeat LFTs ^b as soon as possible, preferably within 48-72 hours from awareness of the abnormal results. If abnormal lab values are confirmed upon the repeat test, then monitor LFTs ^b weekly, or more frequently if clinically indicated, until resolved to $\leq 3.0 \times$ ULN Discontinue patient from the study treatment if elevation is combined with any of the following: 
• Clinical symptoms of liver injury or evidence for hepatic decompensation• Progressively increasing LFTs^b upon repeat testing• Persistence for ≥ 4 weeks
> 5.0 - 10.0 x ULN	Mandatory: Interrupt dose. Repeat LFTs ^b as soon as possible; preferably within 48-72 hours from awareness of the abnormal results. Monitor LFTs ^b weekly, or more frequently if clinically indicated until resolved to $\leq 3.0 \times$ ULN then:

Dose modifications for ETB115	
> 10.0 - 20.0 x ULN	If resolved in \leq 14 days, maintain dose level If resolved $>$ 14 days, decrease one dose level ^e Mandatory: Interrupt dose. Repeat LFTs ^b as soon as possible, preferably within 48-72 hours from awareness of the abnormal results. Monitor LFTs ^b weekly, or more frequently if clinically indicated until resolved to \leq baseline. Then decrease one dose level ^e .
> 20.0 x ULN	Mandatory: Discontinue patient from study drug treatment. Repeat LFTs ^b as soon as possible, preferably within 48-72 hours from awareness of the abnormal results. Monitor LFTs ^b weekly, or more frequently if clinically indicated until resolved to \leq baseline or stabilization over 4 weeks.
Combined^c elevations of AST or ALT and total bilirubin	
For patients with normal baseline ALT and AST and total bilirubin value, [AST or ALT $>$ 3.0 \times ULN] combined with [total bilirubin $>$ 2.0 \times ULN] without evidence of cholestasis ^d OR For patients with elevated baseline AST or ALT [AST or ALT $>$ 3 \times baseline] OR [AST or ALT $>$ 5.0 \times ULN], whichever is lower, combined with [total bilirubin $>$ 2 \times baseline AND $>$ 2.0 \times ULN]	Mandatory: Permanently discontinue patient from study drug treatment. Repeat as soon as possible, preferably within 48 hours from awareness of the abnormal results, then with weekly monitoring of LFTs ^b , or more frequently if clinically indicated, until AST, ALT, or bilirubin have resolved to baseline or stabilization over 4 weeks.

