
All dose modifications should be based on the worst preceding toxicity.
 
^a Common Toxicity Criteria for Adverse Events (CTCAE Version 4.03)
 
^b Core LFTs consist of ALT, AST, GGT, total bilirubin (fractionated [direct and indirect], if total bilirubin $>$ 2.0 \times ULN), and alkaline phosphatase (fractionated [quantification of isoforms], if alkaline phosphatase $>$ 2.0 \times ULN.)
 
^c "Combined" defined as total bilirubin increase to the defined threshold concurrently with ALT/AST increase to the defined threshold
 
If combined elevations of AST or ALT and total bilirubin do not meet the defined thresholds, please follow the instructions for isolated elevation of total bilirubin and isolated elevation of AST/ALT, and take a conservative action based on the degree of the elevations (e.g. discontinue treatment at the situation when omit dose is needed for one parameter and discontinue treatment is required for another parameter). After all elevations resolve to the defined thresholds that allow treatment re-initiation, re-start the treatment either at the same dose or at one dose lower if criterion for dose reduction is met.
 
^d "Cholestasis" defined as ALP elevation ($>$2.0 xULN and R value $<$2) in patients without bone metastasis, or elevation of ALP liver fraction in patients with bone metastasis. The R value is calculated by dividing the ALT by the ALP, using multiples of the ULN for both values. It denotes whether the relative pattern of ALT and/or ALP elevation is due to cholestatic (R \leq 2), hepatocellular (R \geq 5), or mixed (R $>$2 and $<$ 5) liver injury.
 
^e "One dose level" defined as eltrombopag dose reduction by 25 mg.
	

Eltrombopag can cause hepatobiliary laboratory abnormalities, severe hepatotoxicity, and potentially fatal liver injury. Serum ALT, AST and bilirubin should be measured prior to initiation of eltrombopag, every 2 weeks during the dose adjustment phase and monthly after establishment of a stable dose. Abnormal serum liver tests should be evaluated with repeat testing as described in [Table 6-7](#). If the abnormalities are confirmed, serum liver tests should be monitored weekly until the abnormalities resolve, stabilize, or return to baseline levels.

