Both eltrombopag and cyclosporine can cause liver enzyme elevations. In the event that it is impossible to separate the effects of eltrombopag from the effects of cyclosporine, in order to protect patient safety, both drugs must be adjusted or interrupted until the liver normalizes, regardless of which drug may be responsible.

In the case of clinically significant elevated liver enzymes and/or bilirubin levels, a blood sample for the determination of cyclosporine blood concentrations must be collected, as per cyclosporine label. Cyclosporine dose must be decreased by 25% to 50% depending on cyclosporine blood concentrations and to control adverse events, including clinically significant lab abnormalities, in accordance with guidance provided in the cyclosporine label.

Discontinuation of cyclosporine must be considered if liver enzymes and/or bilirubin levels do not normalize within 4 weeks after dose modification or after two sequential dose decreases.

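### Table 6-7 and Section 6.3.4.1 of the Protocol give competing instructions on when liver signals end eltrombopag, and no text says which prevails (minor)

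*Protocol*

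**What the plan says.** **Table 6-7 (Protocol 6.3.1.1), combined elevations.** Two groups lead to mandatory permanent discontinuation.
- Row 1, "For patients with normal baseline ALT and AST and total bilirubin value": AST or ALT above 3xULN with bilirubin above 2xULN, "without evidence of cholestasis".
- Row 2, "For patients with elevated baseline AST or ALT": AST or ALT above 3xbaseline or above 5xULN, whichever is lower, with bilirubin above 2xbaseline and above 2xULN. This row has no cholestasis condition.

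**Footnote c** covers combined rises below these thresholds. The site follows the isolated rows and is told to "take a conservative action based on the degree of the elevations". Once values resolve, it may "re-start the treatment either at the same dose or at one dose lower".

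**Table 6-7, isolated rows.**
- AST/ALT above 3 and up to 5xULN: keep the dose, but stop for symptoms, progressive rise or persistence of at least 4 weeks.
- AST/ALT above 5 and up to 10xULN: interrupt, then same dose if resolved within 14 days, otherwise one level lower.
- AST/ALT above 10 and up to 20xULN: interrupt, then one level lower.
- Bilirubin above 1.5 and up to 3xULN: interrupt and resume. If the rise "is due to the indirect (non-conjugated) component only, no changes to dose are required".

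**Section 6.3.4.1** has three criteria, each leading to immediate discontinuation in the absence of cholestasis.
- Normal baseline: AST/ALT above 3xULN with bilirubin above 2xULN or INR above 1.5.
- Abnormal baseline: "For patients with elevated AST or ALT or TBIL value at baseline: [AST or ALT > 2 x baseline AND > 3.0 x ULN", or AST/ALT above 8xULN, with the same bilirubin condition as row 2.
- Normal baseline ALT: ALT of at least 5xULN, with no bilirubin condition.

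**Section 6.3.1** places mandatory permanent discontinuation in Table 6-7 and Section 7.1.5.1. Section 7.1.5.1 is the replacement policy and lists no events.

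**The concern.** A site that follows Table 6-7 alone can restart eltrombopag in a patient whom Section 6.3.4.1 takes off it. The cross-references favour the table: Section 6.3.1 does not mention 6.3.4.1, and Section 7.2.3 refers DILI to 6.3.1.1. The hepatotoxicity paragraph of Section 6.3.4 points to 6.3.3.2, which deals with infection. The Protocol itself warns of potentially fatal liver injury with eltrombopag, so an unclear stopping rule matters even when few patients meet it.

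**Working it through.** **Inputs.** Section 5.3 excludes AST or ALT above 3xULN and bilirubin above 1.5xULN, so raised baselines up to those limits can enter. I take raised to mean above 1xULN. Let b be the baseline of the raised enzyme in xULN, with the bilirubin condition met and no cholestasis.

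**Step 1. Raised baseline enzyme.**
- Table 6-7 row 2 trigger: min(3b, 5).
- Section 6.3.4.1 trigger: min(max(2b, 3), 8). The 8xULN branch never binds, because 2b is at most 6.

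| b | Table 6-7 | 6.3.4.1 | Difference |
|---|---|---|---|
| 1.1 | 3.3 | 3.0 | 0.3 |
| 1.5 | 4.5 | 3.0 | 1.5 |
| 1.67 | 5.0 | 3.33 | 1.67 |
| 2.0 | 5.0 | 4.0 | 1.0 |
| 2.5 | 5.0 | 5.0 | 0 |
| 3.0 | 5.0 | 6.0 | -1.0 |

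The difference is 3b - 3 up to b = 1.5, then b up to b = 5/3, then 5 - 2b. It peaks at 5/3 = 1.67 and reaches zero at 2.5. Above 2.5 the table stops earlier and nothing in 6.3.4.1 opposes it.

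*Example.* Baseline ALT 1.5 and bilirubin 0.8; on treatment ALT 4.0 and bilirubin 2.5; AST normal and unchanged.
- Bilirubin: 2.5 exceeds 2 x 0.8 = 1.6 and exceeds 2.0, so the condition is met in both texts.
- Section 6.3.4.1: 4.0 > max(3.0, 3.0), so stop.
- Table 6-7: 4.0 < min(4.5, 5), so the combined row is not met. Footnote c then gives keep dose (ALT row) and interrupt with resumption (bilirubin row). The more cautious of these is interruption with a route back.

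**Step 2. Normal baseline ALT.** Take an on-treatment ALT of 6xULN with normal bilirubin and INR and no cholestasis. Section 6.3.4.1 stops the drug (6 is at least 5). Table 6-7 interrupts and returns to the same dose if resolved within 14 days. Between 10 and 20xULN the table still allows restart, one level lower; only above 20xULN does it stop outright. The INR alternative in 6.3.4.1 has no counterpart in the table.

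**Step 3. Raised baseline bilirubin, normal AST/ALT.** Row 1 needs all three normal and row 2 needs a raised enzyme, so neither applies. Section 6.3.4.1 does. With baseline ALT 0.8 and bilirubin 1.2, then ALT 4.5 and bilirubin 2.6, it stops the drug: 4.5 > max(1.6, 3.0), and 2.6 exceeds both 2.4 and 2.0.

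**Step 4. Is eltrombopag dosing finished?** Per SAP Section 1, enrolment was completed on 11-May-2020 and the primary lock was on 09-Dec-2020, which is 212 days. Allowing 21 days of screening leaves 191 days, against 26 x 7 = 182 days of eltrombopag.

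**The case against.** **Both texts can be obeyed by stopping whenever either applies.** This is the sensible reading, and nothing makes 6.3.4.1 subject to the table. But it is not written, and footnote c gives a contrary route. Its call for caution chooses only among the isolated rows. Section 6.3.1.1 adds that, when the two drugs' effects cannot be separated, "both drugs must be adjusted or interrupted until the liver normalizes". That limits the indirect-bilirubin note, but it is still not permanent discontinuation.

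**Some differences are not opposing orders.** This stands. A reader might infer that the texts contradict each other for every abnormal-baseline patient. They do not. Above baseline 2.5xULN, and for cholestatic patients under row 2, one text stops the drug and the other merely adds no stop. Raised baseline bilirubin with normal enzymes is a gap in the table, which 6.3.4.1 fills.

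**Table 6-7 has its own safeguards.** The 3 to 5xULN row stops for symptoms, progression or persistence, and restart requires all elevations to resolve. These narrow the problem but do not remove it.

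**SAE reporting is not ambiguous.** Correct: the trigger for reporting potential DILI sits only in 6.3.4.1.

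**A single merged threshold would be tidier.** A reader might infer this, for example 2xbaseline and 3xULN, or 5xULN, for all abnormal baselines. It would release patients who must stop today. Take baseline AST 1.5, ALT 0.5 and bilirubin 0.8, then ALT 2.5, AST 2.0 and bilirubin 2.5. Row 2 stops this patient (2.5 > 3 x 0.5 = 1.5), but the merged rule would not, since both enzymes are below 3.0. Adding a cholestasis exemption to row 2 would also release patients: baseline ALT 1.5 and bilirubin 0.8, then ALT 4.8, bilirubin 2.5 and ALP 2.6 (R = 4.8/2.6 = 1.85) is stopped now because 4.8 > 4.5.

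**Conclusion.** The point holds, as a minor one. Two mismatches carry competing instructions: raised baseline AST/ALT above 1 and below 2.5xULN with a bilirubin rise (gap up to 1.67xULN), and normal baseline ALT reaching 5xULN or more. The missing INR alternative and the missing row for raised baseline bilirubin are gaps in the table.

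This rests on reading discontinuation in 6.3.4.1 as permanent. The Protocol glossary defines it so and 6.3.4.1 offers no restart, although Table 6-2 uses the word for a one-week pause. The documents give no count of patients in these ranges, so none is projected; I judge it to be few.

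A reader might infer that trial results or current dosing are at risk. The documents do not support that. The response definitions and success criteria do not use these rules, and the liver summaries in SAP Section 2.7.3 use fixed ULN multiples. Eltrombopag treatment is complete by the SAP's dates. Nor do the documents show that any patient was restarted wrongly.

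**What to change.** 1. Keep both sets of thresholds. State in Section 6.3.1, Table 6-7 and Section 6.3.4.1 that eltrombopag is permanently discontinued if either a mandatory-discontinuation criterion of Table 6-7 or, absent cholestasis, a criterion of 6.3.4.1 is met.
2. Make footnote c, the isolated AST/ALT rows and the two indirect-bilirubin notes subject to 6.3.4.1.
3. In Section 6.3.1, replace the reference to 7.1.5.1 with 6.3.1.2, which lists the other permanent-discontinuation events, and 6.3.4.1.
4. Leave row 2 as it is: no merged threshold and no cholestasis exemption.

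The cost is wording only, with no new procedures or data. The downside is that a few more patients may stop eltrombopag permanently, including those with normal baseline ALT who now could restart after a rise to 5xULN or more. For this trial, a note in the clinical study report describing both rules is enough, together with corrected text for any later protocol that reuses these sections.

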6.3 Dose modifications

6.3.1 Dose modification and dose delay

For patients who do not tolerate the protocol-specified dosing schedule, dose interruptions and/or reductions are mandated in order to allow patients to continue the study treatment.

These dose modifications are summarized in [Table 6-7](#). Deviations to mandatory dose interruptions and/or reductions are not allowed. Permanent treatment discontinuation is mandatory for specific events indicated as such in [Table 6-7](#) or listed in [Section 7.1.5.1](#).

These dose changes must be recorded on the Dosage Administration Record – electronic case report form (eCRF).

Common Terminology Criteria for Adverse Events Version 4.03 will be used for this study.

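### Protocol 6.3.4.1 and Table 6-7 give different actions for isolated ALT of 5.0 to 20.0 x ULN with normal baseline ALT: contradictory at exactly 5.0, unresolved on re-start above it

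*Protocol*

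**What the plan says.** **Protocol 6.3.4.1** lists three criteria, any one of which is enough.
- The first pairs a transaminase rise with a bilirubin rise and adds an INR arm: "OR [INR > 1.5] without evidence of cholestasis (no ALP elevation".
- The second covers raised baseline values.
- The third, "For subjects with normal baseline ALT", needs only ALT of at least 5.0 x ULN, with no bilirubin or INR condition.

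The action is "In the absence of cholestasis, these patients must be immediately discontinued from study drug treatment". No re-start rule follows.

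**Table 6-7 (6.3.1.1)**, for isolated AST or ALT:
- Above 3.0 and up to 5.0 x ULN: keep the dose. The exception is "Discontinue patient from the study treatment if elevation is combined with any of the following": clinical signs of liver injury or decompensation, progressively rising tests, or persistence for 4 weeks or more.
- Above 5.0 and up to 10.0: "Mandatory: Interrupt dose". After resolution to 3.0 x ULN or below, resume at the same level if this took no more than 14 days, otherwise one level lower.
- Above 10.0 and up to 20.0: interrupt, then one level lower after return to baseline.
- Above 20.0: discontinue.

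The combined AST/ALT and bilirubin row says "Permanently discontinue patient from study drug treatment".

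**Section 6.3.1** adds "Deviations to mandatory dose interruptions and/or reductions are not allowed" and "Permanent treatment discontinuation is mandatory for specific events indicated as such in" Table 6-7 or listed in 7.1.5.1. It does not name 6.3.4.1. The **glossary** defines study treatment discontinuation as a permanent stop.

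**The concern.** Both texts use mandatory wording for the same laboratory result, so a site that follows one may breach the other. One patient with a given ALT could be kept on dose or re-started, and another with the same ALT stopped for good. The eltrombopag exposure, interruption and discontinuation summaries in SAP 2.4.1 would then partly reflect which section a site happened to follow. Section 6.3.4.1 also starts the work-up that can lead to SAE reporting as potential drug-induced liver injury. A site working from Table 6-7 alone could miss that step.

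**Working it through.** The plan states no figure to reproduce. The check sets the two texts side by side and then looks for a ranking rule.

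**1. Isolated ALT, normal baseline, no cholestasis**

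| ALT (x ULN) | Table 6-7 | 6.3.4.1, third criterion | Compatible? |
|---|---|---|---|
| 4.9 | keep dose (listed exceptions) | not triggered | yes |
| 5.0 | keep dose (listed exceptions) | discontinue at once | no |
| 5.1, 8, 10 | interrupt, then same or one lower level | discontinue at once | differ on re-start |
| 10.1, 20 | interrupt, then one lower level | discontinue at once | differ on re-start |
| 20.1 | discontinue | discontinue at once | yes |

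The difference on whether to stop is therefore one value, 5.0. The difference on re-start covers the range above 5.0 up to 20.0.

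**2. Is the 6.3.4.1 stop permanent?** The glossary, the lack of any re-start rule in 6.3.4.1, and Table 6-7's separate use of interrupt and discontinue say yes. Against this, Table 6-2 and 6.3.1.2 use discontinue for temporary stops (each time with a qualifier), and Table 6-7 adds the word permanently only in the combined row.

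**3. Does any text rank the two?**
- 6.3.1 binds sites to Table 6-7 but is silent on 6.3.4.1. Its other pointer, 7.1.5.1, is the replacement policy and lists no events.
- The conservative-action note under Table 6-7 covers only combined elevations below the combined thresholds.
- Section 2.4 refers dose changes for toxicity to Table 6-7, and 7.2.3 points DILI cases to 6.3.1.1 for a PK sample. Neither ranks the sections.

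**4. Does the cholestasis exception absorb the conflict?** Cholestasis needs ALP above 2.0 x ULN and R = ALT/ALP below 2, so ALP must exceed ALT/2. That is above 2.5, 5 and 10 x ULN at ALT of 5, 10 and 20. The exception is narrow.

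**5. Combined trigger, raised baseline transaminase.** Let b be that enzyme's own baseline in x ULN; exclusion criterion 5 gives b at most 3.
- 6.3.4.1: max(2b, 3). Its 8.0 x ULN limb never binds, since 2b is at most 6.
- Table 6-7: min(3b, 5).

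| b | 6.3.4.1 | Table 6-7 | Gap |
|---|---|---|---|
| 1.0 | 3.0 | 3.0 | 0 |
| 1.2 | 3.0 | 3.6 | 0.6 |
| 1.5 | 3.0 | 4.5 | 1.5 |
| 1.67 | 3.33 | 5.0 | 1.67 |
| 2.0 | 4.0 | 5.0 | 1.0 |
| 2.25 | 4.5 | 5.0 | 0.5 |
| 2.5 | 5.0 | 5.0 | 0 |

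The gap is 3b - 3 up to b = 1.5, then b up to 1.67, then 5 - 2b. It is positive throughout 1.0 < b < 2.5, with 6.3.4.1 lower. At b = 3 the order reverses (6.0 against 5.0). Inside the gap, the Table 6-7 footnote falls back on the isolated rows. These may allow re-start, but not always: subject to the indirect-bilirubin note, they discontinue at bilirubin above 10 x ULN, or at 3 to 10 x ULN unresolved after 14 days.

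**6. INR arm.** Read as AST or ALT above 3.0 x ULN with INR above 1.5, it discontinues, whereas the Table 6-7 row for 3.0 to 5.0 x ULN keeps the dose unless its conditions apply.

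**7. Timing.** SAP section 1 gives end of enrolment as 11-May-2020 and the primary lock as 09-Dec-2020: 212 days. Screening of 21 days plus 26 weeks of eltrombopag is 21 + 182 = 203 days. Planned eltrombopag dosing was therefore over by the lock, even counting from consent.

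**The case against.** The strongest reply is that above 5.0 x ULN both texts withdraw the drug at once, and they conflict only if the 6.3.4.1 stop is permanent. Section 6.3.1 confines mandatory permanent discontinuation to Table 6-7 and 7.1.5.1, and the combined row needed the extra word permanently. This stands in part. A reader might infer a proven contradiction over the whole range from 5.0 to 20.0 x ULN, but the uneven wording does not support that: it is certain at 5.0 and conditional above.

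A reader might also infer that affected patients cannot be traced. That goes too far. Section 6.3.4.1 requires confirmed cases without another cause to be reported as SAEs under a fixed term. Section 8.1.1 records the action taken for each adverse event, separating interruption from permanent discontinuation, and SAP 2.7.1 tabulates both. What remains uncovered is unconfirmed cases, cases with another cause, and patients kept on dose. The SAP 2.7.3 liver rows do not isolate the group: they pool ALT with AST, do not split by baseline, start above 5 rather than at 5.0, and carry no INR.

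The group may also be small. The background section reports that all four patients with ALT above 5 x ULN in ETB115AUS28T, and the one such case in ETB115E1201, had raised transaminases at baseline. Those are other populations and settle nothing here.

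Finally, 6.3.4.1 sits under the eltrombopag risks, so its unnamed study drug is probably eltrombopag, and 6.3.1.1 has its own two-drug rule. That makes the drug question a matter of wording.

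**Conclusion.** The point holds as an internal inconsistency in the current protocol text that should be fixed. With normal baseline ALT, isolated elevation and no cholestasis, the contradiction is certain at exactly 5.0 x ULN. Above that, up to 20.0 x ULN, it is a contradiction if the 6.3.4.1 stop is permanent, which the glossary favours, and otherwise an unresolved ambiguity about re-start. The raised-baseline triggers, the INR arm and the cross-references (6.3.1 to 7.1.5.1, and 6.3.4 to 6.3.3.2, which covers infection) are secondary.

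Two larger consequences might be inferred and are not supported. The primary FAS analysis counts responders among all treated patients and is unaffected by which section was applied. Per-protocol membership could matter only if the SAP Table 2-2 deviation for failure to withdraw eltrombopag includes 6.3.4.1 cases, and the SAP does not list the reasons behind that code. The exposure and discontinuation summaries concerned are descriptive, and the documents do not say how many patients met the trigger.

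**What to change.** **Text.** The sponsor must reconcile 6.3.4.1 and Table 6-7 into one set of thresholds and actions, including the raised-baseline triggers and the INR arm. It should state whether the 6.3.4.1 stop is permanent and which drug it covers, consistently with the two-drug rule in 6.3.1.1, and correct both cross-references. Which rule is right is a clinical decision that this review does not make. An amendment would follow Protocol 12.1.

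**Reporting.** For eltrombopag the remedy is retrospective. In the planned hepatic listing (SAP 2.7.3, narrowed to key parameters in SAP section 4), flag every patient who met a 6.3.4.1 criterion. Include normal baseline ALT with ALT of at least 5.0 x ULN and, where INR was measured, the INR arm; 7.2.2.5.1 describes coagulation testing at baseline, so later INR values may be few. Show cholestasis status and the recorded action: maintained, interrupted and re-started, or permanently discontinued. Cross-check against SAEs reported as potential drug-induced liver injury. Note in the final CSR that the two sections differed. Report the action per patient rather than the section followed, because the records described capture only the action.

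**Cost.** Modest programming on data already collected: three baseline-dependent criteria, the R value and INR, linked to dosing. No new procedures or patients.
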